2.7.2 Deaths

All Deaths and on-treatment deaths will be summarized by MedDRA primary system organ class (SOC) and preferred term of the principal cause of death.

2.7.3 Laboratory data

For safety monitoring, the following laboratory parameters will be assessed during the study:

- hematology: hemoglobin, hematocrit, white blood cell (WBC) count with differential, platelet count, red blood cell (RBC) count, mean corpuscular volume (MCV), absolute Neutrophil Count (ANC) and reticulocyte count
- biochemistry: albumin, alkaline phosphatase, total/fractionated bilirubin, calcium, chloride, creatinine, gamma-glutamyl transpeptidase (GGT), fasting glucose, inorganic phosphorus, potassium, total protein, sodium, C-reactive protein, uric acid, lactate dehydrogenase (LDH), urea (BUN), serum glutamic pyruvic transaminase (SGPT)/alanine aminotransferase (ALT), serum glutamic oxaloacetic transaminase (SGOT)/aspartate aminotransferase (AST), creatinine clearance, serum creatinine;
- urinalysis (dipstick): urinary protein/creatinine ratio, pH, specific gravity, urine blood, urine glucose, urine protein, urine bilirubin, urine ketones, and urine leukocyte esterase.

All hematology and biochemistry laboratory values will be converted into standard international (SI) units and categorized according to laboratory normal ranges (low/normal/high). All values reported on the same day will be first averaged and then used as the result for that day.

In addition to the laboratory data measured by the central laboratory, creatinine clearance will be calculated based on two different formulae (Cockcroft-Gault equation, Schwartz formula for pediatric population). All results for creatinine clearance presented will be based on the Cockcroft-Gault/Schwartz formula.

For selected laboratory tests, additional flags for notable ranges as defined in [Table 2-1](#) will be generated. Laboratory values assessed more than 30 days after discontinuation of study medication will be excluded from the analysis.

Table 2-1 Definition of notable ranges for laboratory tests

Laboratory test	Criteria for notable ranges
Platelet count	< 100 x 10 ⁹ /L (extended range <50×10 ⁹ /L)
Absolute neutrophils	< 1.5 x 10 ⁹ /L (extended range <0.5×10 ⁹ /L)
Serum creatinine	> 33% increase from baseline and > ULN at two consecutive measurements at least 7 days apart
Creatinine clearance	<60 mL/min at two consecutive measurements at least 7 days apart (extended range <40 mL/min at two consecutive measurements at least 7 days apart)
Urinary protein/urinary creatinine ratio	> 1.0 (mg/mg) at two consecutive measurements at least 7 days apart
SGOT/ALT and SGPT/AST	>5 x ULN and 2 x baseline (extended range >10×ULN and >2×baseline value)

The number and percentage of patients with post-baseline laboratory results (scheduled and unscheduled) meeting the criteria for notable values (see [Table 2-1](#)) will be displayed in a

frequency table, by quarter A patient with a notably abnormal value of serum creatinine, or creatinine clearance will be counted in the period during which the second of the two consecutive abnormally high (or low) measurements occurred.

All notable laboratory abnormalities will be listed.

- Shift tables will be generated for each hematology and biochemistry test, cross-tabulating normal/notable/extended ranges baseline laboratory values against worst postbaseline values.
- Listing of all laboratory data with values flagged to show the corresponding normal/notable/extended ranges

Furthermore, observed values and changes from baseline (absolute and relative to baseline) will be summarized for each laboratory test with descriptive statistics quarterly (baseline, Quarter 1, Quarter 2 etc.). If a time period included more than 1 test result from central lab for serum creatinine, the average will be analyzed. For others, if a time period included more than 1 test result from central or local lab, the average will be analyzed.

Boxplots over time will be generated for selected laboratory test (see [Table 2-1](#)). Data will be summarized by period and presented at the midpoint of the respective period. If a time period included more than 1 test result, the average will be analyzed.

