5.3 Exclusion criteria

Patients eligible for this study must not meet **any** of the following criteria:

- Patients diagnosed with HbS-beta Thalassemia
- Anticipated regular transfusion program during the study. Patients having a sporadic transfusion (e.g. in case of infection) during the course of the study will not be excluded
- Any blood transfusion 6 months prior to study start
- Patients unable to undergo study assessments including MRI, e.g. who are claustrophobic to MRI, have a cardiac pacemaker, ferromagnetic metal implants other than those approved as safe for use in MR scanners (Example: some types of aneurysm clips, shrapnel), and patients who are obese (exceeding the equipment limits)
- Significant proteinuria as indicated by a urine protein/urine creatinine ratio > 1.0 mg/mg in a non-first void urine sample at visit 1 or visit 2 (or alternatively in two of three samples obtained for screening)
- Creatinine clearance ≤ 40 ml/min on two measurements during visit 1 and visit 2
- Serum creatinine $> \text{ULN}$ on two measurements during visit 1 and visit 2
- ALT $> 5 \times \text{ULN}$ at visit 1 and visit 2
- Clinical evidence of active hepatitis B (positive HBsAg with negative HBsAb) or hepatitis C (positive HCV antibody and detectable HCV RNA with ALT above the normal range) (Note: Hepatitis B carriers will be allowed to enter the trial.)
- Known diagnosis of cirrhosis (confirmed by biopsy if available)

- A history of clinically relevant ocular and/or auditory toxicity related to iron chelation therapy
- History of positive HIV serology (ELISA or Western blot)
- Presence of a surgical or medical condition that might significantly alter the absorption, distribution, metabolism or excretion of the study drug
- Patients with active inflammatory diseases that interferes with the accurate measurement of serum ferritin
- Pregnant or breast feeding patients, or patients of child-bearing potential not employing an effective method of birth control. (See [Women of child-bearing potential](#), below, for further details regarding effective methods of birth control.)
- Patients participating in another clinical trial or receiving a systemic investigational drug within the past 4 weeks or topical investigational drug within the past 7 days of screening
- History of non-compliance with medical regimens or patients who are considered potentially unreliable and/or not cooperative, unwilling or unable to comply with the protocol

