2.3 Patient disposition, demographics and other baseline characteristics

Demographic and baseline characteristics will be summarized by ethnicity group and overall for the FAS.

Demographics include age, age group (<18 years, 18-<50 years, 50-<65 years, \geq 65 years), gender, race. Other baseline characteristics include weight, weight group ($<$ 35 kg, 35-<55 kg, 55-<75 kg, \geq 75 kg), main underlying disease, history of blood transfusion (Yes/No), history of splenectomy (Yes/No), history of chelation therapy (Yes/No), type of last chelation therapy prior to the study, hepatitis B and C status, medical history by MedDRA primary SOC and preferred term, clinically significant abnormality in baseline ECG (Yes/No), abnormality in baseline audiometric test (Yes/No) and (clinically significant/non-significant), abnormality in baseline ocular exam (Yes/No) and (clinically significant/non-significant), baseline LIC, baseline LIC group ($<$ 5, 5- \leq 7, $>$ 7-15, $>$ 15 mg Fe/g dw), baseline serum ferritin, baseline serum ferritin group ($<$ 300, \geq 300-500, $>$ 500-1000, $>$ 1000-2500, $>$ 2500-5000, $>$ 5000 ng/mL), baseline creatinine, baseline creatinine group (\leq upper limit of normal range (ULN), $>$ ULN), baseline creatinine clearance, baseline creatinine clearance group ($<$ 60, 60-<90, 90-<160, \geq 160 mL/min), baseline ALT, baseline ALT group (\leq ULN, $>$ ULN- $5 \times$ ULN, $>$ 5 \times ULN), baseline AST, baseline AST group (\leq ULN, $>$ ULN- $5 \times$ ULN, $>$ 5 \times ULN), urine protein/creatinine ratio (\leq 0.2 mg/mg, $>$ 0.2-1 mg/mg, $>$ 1 mg/mg).

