2.7.4.2 Vital signs

Measurements of vital signs and body weight done more than 30 days after discontinuation of study medication will be excluded from the analysis.

The change from baseline in diastolic blood pressure, systolic blood pressure, pulse rate, and weight will be summarized by scheduled visit with n, mean, SD, minimum, median, and maximum values. Furthermore, the number (%) of patients with notably abnormal vital signs or weight will be presented by visit and for time point 'at any time after baseline'.

The criteria for notably abnormal vital signs and weight are displayed in [Table 2-2](#).

Table 2-2 Definition of notable ranges for vital signs and weight

Parameter	Criteria for notable ranges
Systolic blood pressure	≥ 180 mmHg / ≤ 90 mmHg with increase / decrease from baseline of ≥ 20 mmHg
Diastolic blood pressure	≥ 105 mmHg / ≤ 50 mmHg with increase / decrease from baseline of ≥ 15 mmHg
Pulse rate	≥ 120 bpm / ≤ 50 bpm with increase / decrease from baseline of ≥ 15 bpm
Weight	$\geq 7\%$ increase or decrease from baseline weight

The vital sign data of patients with notably abnormal vital signs will be listed. Similarly body weight data of patients with notably abnormal body weight will be listed.

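### The quarterly notable-laboratory table has no baseline condition for platelets, neutrophils or creatinine clearance, so its percentages mix entry status with new onset

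*SAP*

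**What the plan says.** SAP 2.7.3 defines the table through this count: "The number and percentage of patients with post-baseline laboratory results (scheduled and unscheduled) meeting the criteria for notable values". It is shown by quarter and, under SAP 2.1, for Chinese, non-Chinese and all patients. The criteria are in SAP Table 2-1:

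- Platelets: "< 100 x 10 ⁹ /L (extended range <50×10 ⁹ /L".
- Neutrophils: "< 1.5 x 10 ⁹ /L (extended range <0.5×10 ⁹ /L".
- Creatinine clearance: "<60 mL/min at two consecutive measurements at least 7 days apart", with an extended range below 40 on the same two-value rule. The patient is assigned to the quarter of the second low value.
- Serum creatinine, by contrast: "> 33% increase from baseline and > ULN at two consecutive measurements at least 7 days apart". ALT and AST also carry a multiple of baseline.

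The vital-sign criteria in SAP Table 2-2 pair an absolute limit with a change, for example systolic pressure "with increase / decrease from baseline of ≥ 20 mmHg".

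On entry, Protocol 5.3 excludes "Creatinine clearance ≤ 40 ml/min on two measurements during visit 1 and visit 2". Sections 5.3 and 5.4 set no platelet or neutrophil limit, and Protocol 6.2 permits hydroxyurea. SAP 2.3 plans a "baseline creatinine clearance group" summary whose lowest category is below 60 mL/min.

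**The concern.** Three of the tabulated tests can be met by a patient whose value has not changed since entry. A patient with clearance 52 mL/min at baseline and 53 on drug appears as notable although nothing has worsened. The plan avoids this elsewhere: in the creatinine, ALT/AST and vital-sign criteria, in limiting adverse-event summaries to events that began or worsened on treatment (SAP 2.7.1), and in flagging new or worsened ECG, ocular and hearing findings (SAP 2.7.4.1). It gives no reason for treating these three tests differently.

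Renal effects and cytopenia are recognised risks of the drug (Protocol 6.4.4 and 6.4.13). The protocol also says that most cytopenia reports came from patients with prior haematological disorders, so entry status has to be separated out. There is no control arm against which to compare the background. A baseline imbalance between the ethnicity groups could also look like a safety difference in this table.

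**Working it through.** The plan states no figure for this point, so there is none to reproduce. The check has three steps.

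**1. Can an eligible patient start below 60 mL/min?** SAP 5.2 gives Cockcroft-Gault as (140 − age) × weight / (0.815 × SCr), multiplied by 0.85 for women, with the values below taking SCr in µmol/L. Two invented patients:

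- Woman, 60 years, 45 kg, SCr 70: 80 × 45 × 0.85 / (0.815 × 70) = 3060 / 57.05 = 53.6 mL/min.
- Man, 65 years, 50 kg, SCr 90: 75 × 50 / (0.815 × 90) = 3750 / 73.35 = 51.1 mL/min.

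Both are above 40 and below 60. Protocol 5.3 also excludes serum creatinine above the upper limit of normal on two measurements. The documents give no numeric limit, so I assume that these values do not exceed it.

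**2. How often is a stable patient counted?** I simulated 20,000 patients per setting with no drug effect, over the SAP's 20 quarters with three or four four-weekly visits each. Visit noise was independent and normal around a constant level, with no drop-out. Clearance needed two consecutive low values and was assigned to the quarter of the second. The levels and the within-patient coefficients of variation (CV) are assumptions, because the documents give none.

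Mean number of quarters flagged, out of 20:

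| Constant level | CV 5% | CV 10% | CV 15% |
|---|---|---|---|
| Clearance 45 | 20.0 | 20.0 | 20.0 |
| Clearance 50 | 20.0 | 20.0 | 19.5 |
| Clearance 55 | 19.9 | 18.3 | 16.6 |
| Clearance 58 | 17.1 | 14.2 | 13.0 |
| Platelets 85 | 20.0 | 20.0 | 20.0 |
| Platelets 95 | 20.0 | 19.6 | 19.2 |
| Neutrophils 1.3 | 20.0 | 20.0 | 19.9 |

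Every simulated patient was flagged at least once. The share flagged in all 20 quarters was 91%, 19% and 3% at clearance 55 (CV 5%, 10%, 15%), and 5%, 0.2% and 0% at clearance 58.

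**3. What does each such patient add?** SAP 1 gives 134 enrolled (68 Chinese, 66 non-Chinese). With k patients low at entry and staying low, the addition to a quarter is k/134:

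- k = 1: 0.7%
- k = 5: 3.7%
- k = 10: 7.5%

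k is assumed, and 134 is the number enrolled, not a confirmed Safety Set size. One patient within an ethnicity group adds 1/68 or 1/66, about 1.5%. The denominator can also shrink: 112 were still on treatment at the one-year analysis, and 1/112 = 0.9%.

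**The case against.** The strongest reply is that the plan already shows baseline status elsewhere and that this table never claims to be incidence. Much of that stands.

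- SAP 2.7.3 plans shift tables of baseline against worst post-baseline category for each haematology and biochemistry test. Platelets and neutrophils have single-value criteria, so the shift table largely separates entry status from worsening over the whole study.
- The same section plans quarterly absolute and relative changes from baseline, and Protocol 10.5.10.3 adds relative change in clearance by category. SAP 2.3 tabulates the baseline clearance groups.
- The serum creatinine and ALT/AST criteria have baseline terms and are unaffected. The urine protein/creatinine cut-off is fixed, but the screening exclusion above 1.0 mg/mg makes a notable baseline unlikely.
- The exclusions for raised creatinine, significant proteinuria and interfering systemic disease, including renal disease, limit how many patients enter with low clearance.
- A quarterly count of patients within a protocol-defined range is a legitimate descriptive display.

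What these displays do not give is a quarterly patient count separated by baseline. The shift table uses one worst value for the whole study, and the change summaries do not count patients. For clearance, SAP 2.1.1 takes baseline as the last value on or before Day 1, and one value cannot meet a two-value rule. Two screening values should exist, but the SAP does not say how to use them for the category.

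A reader might also infer that any single low clearance value is counted, or that every patient low at entry is counted in every quarter. The documents support neither. Clearance needs two consecutive low values, and no rule makes the count repeat. Repetition depends on values staying low and becomes less regular near 60 mL/min.

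**Conclusion.** The point holds for one table and three tests. Patients can enter below the cut-offs, the count ignores this, and a stable patient well below a cut-off is counted in most quarters. The percentages therefore combine existing abnormality with new onset and cannot serve as onset rates, overall or by ethnicity group.

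The size per patient is about 0.7% of 134 in each quarter in which the value stays low. The total depends on the share abnormal at entry, which is not given. A reader might infer a fixed factor by which the table overstates harm. None can be stated, because the documents give neither the entry share nor a new-onset rate. Nor does the evidence show that laboratory safety as a whole is uninterpretable, since the other displays carry baseline information. The repeat-count results rest on the assumed levels, the assumed noise and no drop-out.

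**What to change.** In SAP 2.7.3, keep the existing count and split the rows for platelets, neutrophils and creatinine clearance by whether the baseline value is below the numeric cut-off:

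1. **Not below at baseline:** report newly notable patients, with this number at risk as the denominator.
2. **Already below at baseline:** show a separate row with worsening from baseline. Include change within the notable range as well as progression to the extended range. Simply removing these patients, or counting them only on reaching the extended range, would hide a fall in clearance from 59 to 41 mL/min.
3. **Clearance category:** state that the numeric baseline value sets it, and use the same rule in the shift table.

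This changes reporting only and needs no new data. It costs a short SAP addition, a baseline flag in programming, a few more rows, and denominators that differ by test. Setting the clearance category from one value remains a simplification against the two-value on-treatment rule, which a footnote should say.

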2.7.4 Other safety data

Data from vital signs, body weight, ECG, ocular, and auditory examination will be listed and summarized with descriptive statistics as appropriate. Any significant findings after start of study will be documented as AEs and reported as such.

2.7.4.1 ECG, audiometric test and ocular examination

ECG, audiometric test, ocular examination and echocardiography will be performed at baseline, Week 52 and Week 260. Abnormalities will be reported together with an overall interpretation of the findings. Any abnormalities at baseline will be summarized. At Week 260, the investigator flagged all abnormalities which will be new or worsened since baseline. All new or worsened abnormalities are recorded on the AE CRF page. All findings of patients with new or worsened clinically significant abnormalities will be listed.

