7.2.2.4 Auditory and ocular examination

Patients will undergo auditory and ocular examinations at screening and weeks 52, 104, 156, 208, 260 and at unscheduled visits (if needed).

The auditory examination includes the following assessments:

- Comprehensive audiometry threshold examination
- Speech recognition

The ophthalmologic examination includes the following assessments:

- Visual acuity test
- Tonometry
- Slit lamp exam of anterior segment
- Slit lamp exam of the lens
- Fundoscopic and retinal examination

Information about the audiometry and ocular examinations must be present in the source documentation at study site. Significant findings of the audiometry and ocular examinations that meet the definition of an AE must be recorded in the adverse event summary page of the case report form.

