7.2.2.6 Cardiac assessments

7.2.2.6.1 Electrocardiogram (ECG)

A standard 12 lead ECG will be performed at Screening and annually throughout the study (weeks 52, 104, 156, 208, and 260). Interpretation of the tracing must be made by a qualified physician and documented on the ECG CRF page. Each ECG tracing must be labeled with the study number, patient initials (where regulations permit), patient number, date, and kept in the source documents at the study site. Clinically significant abnormalities present when the patient signed the Informed Consent form must be reported on the Medical History CRF page. Clinically significant findings must be discussed with the Novartis Medical Monitor prior to enrolling the patient in the study. New or worsened clinically significant findings occurring after informed consent must be recorded on the Adverse Events CRF page.

[figure not shown]

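### SAP 2.7.4.1 names only Weeks 52 and 260 for the ECG, hearing and eye examinations that the protocol schedules every year, and describes the new-or-worsened flag at Week 260 alone (minor, but wrong as written)

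*SAP*

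**What the plan says.** SAP 2.7.4.1 gives the timing in one sentence: "ECG, audiometric test, ocular examination and echocardiography will be performed at baseline, Week 52 and Week 260". It then says: "At Week 260, the investigator flagged all abnormalities which will be new or worsened since baseline". On recording, it says: "All new or worsened abnormalities are recorded on the AE CRF page". It promises a summary of baseline abnormalities, and a listing of all findings for patients whose new or worsened abnormalities are clinically significant.

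The protocol's current text sets a different schedule. Section 7.2.2.4 says: "Patients will undergo auditory and ocular examinations at screening and weeks 52, 104, 156, 208, 260", and also allows unscheduled examinations. Section 7.2.2.6.1 places the ECG at screening and then "annually throughout the study (weeks 52, 104, 156, 208, and 260". The audiometry row of Table 7-1 agrees: Weeks 52, 104, 156 and 208, plus a mark in the Week 260/EoT column (Visit 777).

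The protocol is also narrower on what reaches the adverse event page. For hearing and eyes: "Significant findings of the audiometry and ocular examinations that meet the definition of an AE must be recorded". For ECG: "New or worsened clinically significant findings occurring after informed consent must be recorded on the Adverse Events CRF page".

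SAP Section 1 states that this plan covers all data up to the last patient's last visit. SAP Section 4 declares no change from the protocol's analyses.

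**The concern.** SAP 2.7.4.1 is the only place in the SAP that gives visits for these examinations, and its list does not match the protocol. The flag that identifies new or worsened findings is described only at the last visit, so the text does not say how findings at the intermediate yearly visits are to be classified.

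What is at stake is the Year 2 to 4 picture. Hearing loss and lens opacities are named effects of the drug (protocol 1.2.1.2 and 6.4.11), and 6.4.11 recommends testing every 12 months. Long-term safety is why the study was extended to five years. An abnormality that appears at Week 104, 156 or 208 and has gone by the final visit is what yearly examinations can show and an end-of-study comparison cannot. No efficacy result is involved.

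**Working it through.** No figure in the plan needs reproducing. The check compares the visit lists and then follows where each kind of finding would be reported.

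**Step 1: the lists side by side**

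| Post-baseline time point | Protocol 7.2.2.4 (hearing, eye) | Protocol 7.2.2.6.1 (ECG) | Table 7-1, audiometry row | SAP 2.7.4.1, examination | SAP 2.7.4.1, flag |
|---|---|---|---|---|---|
| Week 52 | yes | yes | yes | yes | no |
| Week 104 | yes | yes | yes | no | no |
| Week 156 | yes | yes | yes | no | no |
| Week 208 | yes | yes | yes | no | no |
| Week 260 | yes | yes | yes (EoT, Visit 777) | yes | yes |

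**Step 2: counts**

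- Protocol {52, 104, 156, 208, 260} minus SAP {52, 260} leaves {104, 156, 208}: 3 of 5 sets, or 60%, are not named.
- The flag is described at 1 of 5 visits, so 5 − 1 = 4 of 5, or 80%, fall outside it.
- The longest gap between named examinations is 260 − 52 = 208 weeks in the SAP, against 52 weeks in the protocol.

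**Step 3: where a finding first seen at Week 104, 156 or 208 would be reported**

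- *Clinically significant.* The protocol sends it to the adverse event page if it meets the adverse event definition, and SAP 2.7.1 tabulates it. It is reported whether or not it resolves.
- *Not significant, still present at the final visit.* The last examination and the flag at that visit pick it up.
- *Not significant, resolved before the final visit.* It stays in the general listing under SAP 2.7.4. The flag as described does not reach it. The protocol does not require an adverse event entry, although the SAP sentence says every new or worsened abnormality has one. Whether it enters a summary depends on how the open wording of SAP 2.7.4 is applied.

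The third path is the exposed group. A related case is a significant finding that has resolved by the final visit. It reaches the adverse event tables, but it could miss the special listing in SAP 2.7.4.1 if membership of that listing rests on the Week 260 flag.

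**Step 4: are the data there to fix it?** Audiometry is a database item in Table 7-1, and protocol Amendment 1 records the same category for ocular examinations. For ECG: "Interpretation of the tracing must be made by a qualified physician and documented on the ECG CRF page". Whether the new-or-worsened flag itself was collected at Weeks 52 to 208 cannot be told from the documents.

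**The case against.** The strongest reply is that the harm is inferred. The sentence in SAP 2.7.4.1 says when examinations take place, and the section specifies no post-baseline table at any week. SAP 2.7.4 and protocol 10.5.10.4 both put these data in listings and summaries without limiting the visits. On that reading, 2.7.4.1 contains an outdated procedural sentence and no exclusion rule. This largely stands. A reader might infer that results from Years 2 to 4 would be dropped, or that only Weeks 52 and 260 could be tabulated; the documents do not say so.

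A second reply is that, by the SAP's own words, every new or worsened abnormality is an adverse event, which would leave nobody exposed. This stands only in part, because the protocol required sites to record significant findings only.

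A third concerns the label. A reader might infer that naming Week 260 without EoT leaves out early leavers, since 134 − 112 = 22 patients (16%) were off treatment at the one-year analysis. The documents do not support that. Table 7-1 puts Week 260 under EoT as Visit 777, protocol 7.2.2.4 and 7.2.2.6.1 use the same week label, and protocol 6.5.1 gives patients who stop early the final-visit assessments. Writing EoT out is a clarification.

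Two further inferences also fail. Echocardiography appears in the SAP sentence, but parts of Table 7-1 and Section 7.2.4 cannot be read in the public protocol, so the mention can only be reconciled, not called an error. The creatinine baseline might look ambiguous because protocol 6.4.4 averages Visits 1 and 2. However, SAP 2.1.1 fixes the last value up to Day 1 for all variables except ferritin, and 6.4.4 is a dosing rule.

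**Conclusion.** The mismatch is real and in current text: three of five yearly sets are not named, and four of five fall outside the flag as described. SAP Section 4 records no decision to restrict the visits, so the sentence should be corrected.

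The consequence is minor. The data are not lost, significant findings reach the adverse event tables, and no efficacy conclusion changes. What remains is uncertainty over how abnormalities, mainly non-significant ones not recorded as adverse events, are summarised when they first appear at Weeks 104 to 208 and resolve before the final visit.

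No size can be put on that group. The documents give no rate of onset or resolution, and no share of such findings recorded as adverse events. Counting the examinations done at the three unnamed visits would not measure results missing from the report.

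The conclusion assumes that the ocular and ECG rows of Table 7-1, which cannot be read here, agree with protocol 7.2.2.4 and 7.2.2.6.1.

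**What to change.** In SAP 2.7.4.1:

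- List the time points as baseline and Weeks 52, 104, 156, 208 and 260/EoT. State that the final visit of a patient who leaves early counts as EoT, subject to the 30-day on-treatment window already in SAP 2.1.1.
- Summarise the overall interpretation by visit and once over all post-baseline visits, as SAP 2.7.4.2 does for vital signs. The second summary would also take in unscheduled examinations.
- Apply the new-or-worsened flag at every visit where it was collected. Elsewhere, derive a shift from the baseline category in SAP 2.3, and note that a shift cannot show worsening within a category. For hearing and eyes, SAP 2.3 separates normal, abnormal not significant and abnormal significant. For ECG it names only clinically significant abnormality, yes or no, so that shift is coarser unless the ECG page holds more detail.
- Align the sentence on adverse event recording with protocol 7.2.2.4 and 7.2.2.6.1.
- Reconcile the mention of echocardiography with the full protocol.

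The cost is SAP wording and programming, with no new data.

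Optional and separate: the SAP could align its creatinine analysis baseline with the duplicate-based baseline in protocol 6.4.4 and 7.2.2.5.2, with a footnote on comparability with the one-year report.
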